**Is there a Certificate of Confidentiality in place for this project? (If so, please provide a copy).**

There is no Certificate of Confidentiality in place for this project.

## 12. CONFLICT OF INTEREST

(For information on disclosure reporting see: <http://www.udel.edu/research/preparing/conflict.html> )

**Do you have a current conflict of interest disclosure form on file through UD Web forms? Yes**  
**Does this project involve a potential conflict of interest\*? NO**

\* As defined in the University of Delaware's Policies and Procedures, a potential conflict of interest (COI) occurs when there is a divergence between an individual's private interests and his or her professional obligations, such that an independent observer might reasonably question whether the individual's professional judgment, commitment, actions, or decisions could be influenced by considerations of personal gain, financial or otherwise.

If yes, please describe the nature of the interest:

## 13. CONSENT and ASSENT

Consent forms will be used and are attached for review (see Consent Template under Forms and Templates in IRBNet)

Additionally, child assent forms will be used and are attached.

Waiver of Documentation of Consent (attach a consent script/information sheet with the signature block removed).

Waiver of Consent (Justify request for waiver)

#### 14. Other IRB Approval

**Has this protocol been submitted to any other IRBs?** This study has been approved by the University of Pennsylvania's and Indiana University's IRB and that approval has been submitted as an amendment to this protocol. An Institutional Review Board Authorization Agreement has been signed between CCHS and UD.

#### 15. Supporting Documentation

*Please list all additional documents uploaded to IRBNet in support of this application.*

Appendices which include IRBNet Protocol ID# 619037-1, entitled "Shared Pre-enrollment Process for Stroke Research Team Studies", that is referenced in this protocol, along with copies of specific clinical tests, screening questions and the inclusion/exclusion checklist for this protocol.

A separate Appendix is attached with the example DSMB charter.

# Summary of protocol changes

## Summary of protocol changes

Approval date	Description of protocol changes
3/23/2016	Initial approval
5/1/2017	To exclude individuals who walk at <0.3m/s (due to limitations of Fitbit sensitivity); to ensure consistency in language describing training phase in protocol and consent form
10/16/2018	To add IU as an evaluation and training site
9/28/2020	To add language to consent form to reflect that while risk of COVID-19 exposure will be minimized, the risk of exposure cannot be completely eliminated

**Original statistical analysis plan  
(excerpted from original IRB protocol  
(2016), NIH grant application (2014), and  
published protocol (2018)**

## General data management & analysis

Encrypted electronic files that connect subject identities to their subject code will be stored in a database on a password protected server. Paper copies of consent forms for each site will be stored on-site. Paper copies of the screening form for subjects that sign the Informed Consent are also stored at each site.

The Biostatistician running analyses is blinded to group assignment. An “intent to treat” analysis will be performed. To ensure that the randomization worked, potential covariates (e.g. age, time since stroke, cognition) will be compared between groups using t-tests and  $\chi^2$  tests. If a covariate is significantly different between groups, this will be an indication that the groups are not balanced and the covariate will be included in the models. The alpha is set at 0.05 for primary analyses and .01 for secondary analyses.

Aims 1 & 2 will be tested using General Linear Mixed Models (GLMM). To compare the efficacy of the FAST+SAM, FAST and SAM interventions for improving real-world walking activity in chronic stroke survivors and to determine for whom the interventions are most effective General Linear Mixed Models (GLMM) will be developed. All model assumptions will be tested (including linearity, normality, homoscedasticity, and multicollinearity). Outliers and influential cases will be screened for and removed. Violations of the assumptions will be remedied using transformations or a Generalized Linear Model. Post-hoc tests in the GLMMs will use Bonferroni adjustment and for the regression models post-hoc probing of interactions will be done using simple slopes method.

For the GLMMs, the covariance structure will be chosen using nested model comparisons. The regression models also have the assumptions of homoscedasticity and multicollinearity, which will be tested using the Breusch-Pagan test, and by examining the condition index and variance inflation factor, respectively. To eliminate ignorable collinearity caused by the inclusion of interaction terms, continuous variables will be centered before being entered into the models. Site differences will also be tested, and if differences exist, will be included in the model to control for them.

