## Power analysis & sample size

The precise increase in steps/day necessary to reduce the risk of secondary health complications and disability post-stroke is not known, however, studies in other at risk populations have shown a reduction in cardiovascular events with an increase of 2,000 steps/day. Previous studies in chronic stroke, along with our data, suggest an improvement in ~1000 steps/day with fast walking training alone and our recent study suggests an improvement of ~1100 steps/day with a step activity monitoring program alone. Our data from the FAST+SAM intervention suggests an improvement of ~1700 steps/day in those with low steps/day at baseline and an improvement of ~250 steps/day for those in FAST with low baseline steps/day. Given this, we would consider an average improvement of  $\geq 1700$  steps/day in the FAST+SAM group worthy of further study in future clinical trials. Power calculations indicate that a total of 225 participants

are needed (75 in each of the 3 groups) in order to detect this differential increase based on baseline steps/day and intervention received with power greater than 0.90. These calculations assume equal group sizes, a moderate correlation among repeated measures of  $r=0.50$ , and a standard deviation for steps/day of 2,500.

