### **Expected outcomes and aim specific analysis**

**Aim 1.** To compare the efficacy of the FAST+SAM, FAST and SAM interventions for improving real-world walking activity in chronic stroke survivors and to determine for whom the interventions are most effective. The primary measure for this Aim is number of steps per day (SPD). Data will be calculated at each time point (Baseline, post-treatment, 6 and 12 month follow-up) by finding the average number of SPD over one week.

*H1.1. All 3 interventions will improve real world walking activity immediately post-intervention.*

A GLMM will be used to evaluate changes in SPD from pre- to post-training. For this hypothesis the main effect of time will be compared, averaged across groups. If the main effect of time is significant, this research question can be answered using the marginal pairwise comparisons of SPD at baseline with post-training. If an interaction is significant, the simple main effect of time will be compared between interventions.

**Aim 2.** To compare the efficacy of the FAST+SAM, FAST and SAM interventions for improving walking speed, endurance and cardiorespiratory function in chronic stroke survivors and to determine for whom the interventions are most effective. The primary measure for this Aim is distance covered during the 6 minute walk test (6MWT). The secondary measures for this Aim are self-selected walking speed as measured during the 10 meter walk test (SSWS) and cardiorespiratory function as measured by peak oxygen consumption during graded exercise testing ( $VO_2$  peak). Data will be calculated at each time point (Baseline, post-treatment, 6 and 12 month follow-up).

The same exact analyses used in **Aim 1** for all the hypotheses will be used in Aim 2 but with the outcomes of 6MWT, SSWS and  $VO_2$  peak. Separate models will be completed for the 6 and 12 month time point.

**Updates to statistical analysis plan  
(excerpted from final IRB protocol  
(2023), ClinicalTrials.gov registry (2022))**

**General data management & analysis - all changes from initial plan were to incorporate use of REDCap electronic databases to increase data accuracy, accessibility, and security:**

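### Covariates and site enter the models only after a significance test, and the one printed model names no baseline adjustment; pre-specifying both would be a cheap gain in precision

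*Combined protocol and SAP*

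**What the plan says.** The original SAP, under General data management & analysis, has potential covariates compared between groups by t-tests and chi-square tests. Age, time since stroke and cognition are given only as examples. The rule for model entry is: "If a covariate is significantly different between groups, this will be an indication that the groups are not balanced and the covariate will be included". For site: "Site differences will also be tested, and if differences exist, will be included in the model to control for them". The test for site is not named. The same section says that the biostatistician is blinded to group and that "Post-hoc tests in the GLMMs will use Bonferroni adjustment". It also mentions a second family of models: "for the regression models post-hoc probing of interactions will be done using simple slopes method".

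Under Expected outcomes and aim specific analysis, H1.1 is the only hypothesis whose model is printed. It is a general linear mixed model (GLMM) for steps per day (SPD) from pre- to post-training. The time effect averaged over groups is tested first. Then: "If an interaction is significant, the simple main effect of time will be compared between interventions". No baseline covariate is named, and no constraint of equal baseline means across arms. Aim 2 uses the same analyses "for all the hypotheses will be used in Aim 2 but with the outcomes of 6MWT", self-selected walking speed (SSWS) and VO2 peak.

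The SAP updates report changes to data management only, and none to the aim-specific analyses.

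**The concern.** There are two separate points.

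**The entry rule.** Allocation is random, so a significant baseline difference between arms is a chance event. Whether a covariate sharpens the comparison depends on how strongly it predicts the outcome, and the rule never asks that. A strongly prognostic covariate that happens to be balanced stays out. The final model is fixed by test results, not in advance. The form of entry is not stated either. Entered only as a main effect, a covariate cancels from a pre-post group-by-time contrast with complete data, so in that form the rule would do nothing for an arm comparison.

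**Baseline in the printed model.** The stated objective includes whether FAST+SAM is superior to FAST alone or SAM alone, which is a between-arm question. H1.1's follow-up step is the only printed analysis that could bear on it. If that step compares arms, it compares changes from baseline, which under the plan's own assumptions is less precise than comparing post values adjusted for baseline. Every outcome's baseline is already collected.

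**Working it through.** **Inputs.** From Power analysis & sample size: SD 2,500 steps/day, "a moderate correlation among repeated measures" of r = 0.50, 75 per arm, power above 0.90. Gains are about 1,700 steps/day with FAST+SAM in those with low baseline steps/day, and "an improvement of ~250 steps/day for those in FAST with low baseline steps/day". Alpha is 0.05 for primary analyses; two-sided testing is assumed. The values r = 0.7 and 0.8 and all SD ratios below are sensitivity assumptions.

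**1. The plan's own figure.** With equal variances, SD of change = 2,500 × √(2(1 − 0.50)) = 2,500. SE of an arm difference = 2,500 × √(2/75) = 408. For 1,700 − 250 = 1,450, power = Φ(1,450/408.2 − 1.96) = Φ(1.59) = 0.944. That agrees with the stated power, but only if a difference given for low-baseline participants is applied to all 75 per arm.

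**2. Baseline adjustment, equal variances.** Variance per participant is 2(1 − r)SD² for a change score and (1 − r²)SD² with adjustment. The ratio is (1 + r)/2, so the reduction is (1 − r)/2. SE = √(variance × 2/75).

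| r | SE, change | SE, adjusted | Variance reduction |
|---|---|---|---|
| 0.50 | 408 | 354 | 25% |
| 0.7 | 316 | 292 | 15% |
| 0.8 | 258 | 245 | 10% |

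A simulation with three arms of 75 gave variance ratios of 0.754, 0.855 and 0.904, against 0.75, 0.85 and 0.90 by formula. At r = 0.50 the change-score contrast would need 75/0.75 = 100 per arm to match the adjusted one at 75.

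**3. Unequal variances.** Let s1 be the baseline SD and s2 the post SD. The change-score variance is s1² + s2² − 2r·s1·s2 and the adjusted variance is s2²(1 − r²). Their difference is (s1 − r·s2)², so the reduction is (s1 − r·s2)²/(s1² + s2² − 2r·s1·s2). With r = 0.50 and s2 = 1:

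- s1 = 0.9: 0.16/0.91 = 17.6%
- s1 = 0.8: 0.09/0.84 = 10.7%
- s1 = 0.6: 0.01/0.76 = 1.3%
- s1 = 1.2: 0.49/1.24 = 39.5%

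Eligibility requires fewer than 8,000 steps/day and a walking speed between 0.3 and 1.0 m/s at baseline. Post values are not capped, so s1 below s2 is plausible for SPD and SSWS.

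**4. Incomplete post data.** The original protocol plans 258 recruited and 13% attrition, which gives 86 randomised and about 75 measured per arm. With known covariance, data missing at random and r = 0.50, the SE is 402 with free baseline means and 354 with a common baseline mean. That is 22.5% less variance, so a mixed model that uses incomplete cases does not recover most of the gain by itself.

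**5. How often the entry rule fires.** Three pairwise t-tests at 0.05 are assumed, as the layout is not stated. Simulation (200,000 replicates) flags a given continuous covariate by chance in 12.2% of trials. It therefore stays out in about 88%, however prognostic it is.

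**6. What cannot be computed.** The documents give no correlation between the outcomes and age, time since stroke, cognition or site, so the loss from leaving those out has no number here. They give r for steps/day only, so the table does not carry over to the six-minute walk distance (6MWT), SSWS or VO2 peak without assumption.

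**The case against.** The strongest reply has four parts.

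- **The 25% is not a measure of the covariate rule.** A reader might take it as the cost of the balance-test rule. It is not: it comes from adjusting for the outcome's own baseline, on which H1.1 is silent. This stands, and the two points must be kept apart.
- **H1.1 may contain no arm contrast.** It hypothesises that all three interventions improve walking, and its follow-up step can be read as estimating the pre-post effect within each arm. On that reading the formulas in the working do not apply to it. The wording leaves both readings open.
- **The SAP is an excerpt.** The regression models probed by simple slopes, and a power target framed as a differential increase by baseline steps/day, suggest moderation models that contain baseline steps/day. The gain may already be there. It would be wrong to infer that the plan never adjusts for baseline.
- **The consequence is modest.** The analyst is blinded, which limits selective use of the rule, though not its dependence on the data. Neither analysis is biased.

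A reader might also infer that the trial is underpowered for whole-arm comparisons, by setting 1,700 against the roughly 1,000 quoted for fast walking alone. The documents do not support that. The observed 1,700 belongs to low-baseline participants, and for the whole FAST+SAM group it is a threshold for further study, not an expected mean. The protocol says that it does not expect superiority for all participants.

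**Conclusion.** The concern holds in limited form, with medium confidence. The entry rule for covariates and site selects on chance imbalance and leaves the model to depend on the data. Its cost in precision cannot be sized from the documents.

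The printed model names no baseline adjustment. If its follow-up step compares arms, adjustment would reduce the variance of that contrast by 25% under the plan's single SD and r = 0.50. This rests on complete data and equal baseline and post variances. The figure is an illustration, and 10% to 25% is not a bounding range: the gain shrinks when the baseline SD is below the post SD and grows when it is above.

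H1.1's time effect averaged over groups is unaffected. No shortfall against the stated power is claimed, because the power statement concerns a difference that depends on baseline steps/day and the number of contrasts under Bonferroni is not given.

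**What to change.** - Drop balance tests as a rule for choosing covariates, and report baseline tables descriptively.
- For every between-arm comparison of SPD, 6MWT, SSWS and VO2 peak, pre-specify either the outcome's own baseline as a covariate (ANCOVA) or a common baseline mean across arms in the GLMM.
- Include site and a short named list of prognostic covariates whatever any test shows. Age, time since stroke and cognition are the plan's own examples. Enter them in a form that acts on the arm contrast: ANCOVA, or with time interactions.
- State whether H1.1's follow-up step is within or between arms. Write out the moderation models, say whether baseline SPD is a term, and give the number of contrasts that the Bonferroni adjustment covers.

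H1.1's pooled time effect can stay as it is. The cost is SAP wording and a few degrees of freedom, with no new data. If unblinded analysis has begun, label the adjusted analysis as supplementary.

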Encrypted electronic files that connect subject identities to their subject code will be stored in a database on a password protected UD managed server for the UD and CCHS subjects. Similar processes are in place at UPenn and IU for their subjects. These files are not shared between sites. Paper copies of consent forms for each site will be stored on-site. Paper copies of the screening form for subjects that sign the Informed Consent are also stored at each site.

All coded subject data will be collected and managed using REDCap electronic data capture tools hosted by the University of Delaware's Delaware Rehabilitation Institute. REDCap (Research Electronic Data Capture) is a secure, web-based application designed to support data capture for research studies. All sites will have access to the coded data in the REDCap database.

Data from each evaluation session will be entered directly into the PROWALKS REDCap Clinical database. This database is designed with built in quality control checks (e.g., range checks, checking for missing data for required data points). In addition, each month the UD Research PT will examine frequency distributions of outcome variables to identify questionable data points.

Data from each training session will be entered directly into the PROWALKS REDCap Training database. This database is designed with built in quality control checks (e.g., range checks, checking for missing data for required data points). In addition, each quarter the UD Stroke Studies Coordinator will review a random sampling of data from 6 sessions at each site according to the Treatment Fidelity checklist webform.

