**Expected outcomes and aim specific analysis**

There were no changes to expected outcomes and planned aim specific analysis between the start and end of the study.

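### The SAP promises intent-to-treat but orders outliers and influential cases removed, without limiting this to data errors or planning an all-data analysis

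*Combined protocol and SAP*

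**What the plan says.** Under General data management & analysis, the SAP states: "An “intent to treat” analysis will be performed". The same section then says: "Outliers and influential cases will be screened for and removed". The sentence has no condition attached. It does not mention data errors, a diagnostic, a cut-off, whether a case is one visit value or a whole participant, or whether screening comes before or after any transformation. The next sentence gives a separate remedy for poor fit: "Violations of the assumptions will be remedied using transformations or a Generalized Linear Model". The section also says that the biostatistician is blinded to group.

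The later Updates to statistical analysis plan do not withdraw the rule. For general data management and analysis they report that "all changes from initial plan were to incorporate use of REDCap electronic databases". They add range checks, and a review in which "each month the UD Research PT will examine frequency distributions of outcome variables to identify questionable data points", but do not connect either to removal. On the aims, they state: "There were no changes to expected outcomes and planned aim specific analysis between the start and end of the study". Aim 2 reuses the Aim 1 analyses, so the rule also reaches the 6 minute walk, walking speed and peak oxygen consumption.

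**The concern.** An intent-to-treat analysis should use the valid outcomes of the people randomised. A rule that deletes values for their residual or influence does two things. It shrinks the residual variance that feeds the standard error. It also makes the estimate itself more variable, because the window of retained values is centred on a fitted mean that moves with the data. Tests then reject too often and intervals cover too little. This happens under an automatic rule that ignores arm, so blinding does not prevent it.

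H1.1 carries a second risk. It concerns average change from baseline, and if changes are skewed, cutting the longer tail moves that average even when all arms behave alike. Finally, if a case means a participant, the result no longer covers everyone randomised.

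**Working it through.** **Inputs.** From Power analysis & sample size: 75 per arm, three arms, SD 2,500, correlation 0.50, gains of about 1,700 (FAST+SAM) and 250 (FAST) in participants with low baseline steps. Alpha is 0.05 (General data management & analysis), taken as two-sided. All cut-offs below are assumptions.

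**1. The plan's own figure.** SD of change = 2,500 × √(2 × (1 − 0.5)) = 2,500. SE of a pairwise difference in change = 2,500 × √(2/75) = 408. Difference = 1,700 − 250 = 1,450. Power = Φ(1,450/408.2 − 1.960) = Φ(1.592) = 0.944, consistent with the stated value above 0.90. This applies the low-baseline difference to all 75 per arm. The error rates below do not depend on it.

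**2. Effect of trimming at c residual SDs, normal data.** Let p = 2Φ(c) − 1, a = 2cφ(c), t = p − a. In large samples:

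- reported SE ≈ 408.2 × √t / p
- true SD of the estimate ≈ 408.2 × √(t + 2at + a²) / p
- type I error ≈ 2Φ(−1.96 × reported/true)

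| c | p | a | t | Reported SE | True SD | Type I error |
|---|---|---|---|---|---|---|
| 3 | 0.9973 | 0.0266 | 0.9707 | 403 | 414 | 5.6% |
| 2.5 | 0.9876 | 0.0876 | 0.8999 | 392 | 427 | 7.2% |
| 1.987 | 0.9530 | 0.2203 | 0.7327 | 367 | 450 | 11.0% |

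**3. Simulation, whole participants removed** (10,000 trials; Monte Carlo SE about 0.2 points at 5%; one round of removal, then refit):

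| | All data | 3 SD | 2.5 SD | 1.99 SD |
|---|---|---|---|---|
| Pairwise type I error | 4.7% | 5.5% | 7.4% | 11.1% |
| Any error in three Bonferroni tests | 4.4% | 5.1% | 7.1% | 13.0% |
| H1.1 time effect | 5.1% | 5.6% | 6.8% | 10.8% |
| Coverage of 95% interval | 95.1% | 94.4% | 92.8% | 89.2% |
| Mean number removed of 225 | 0 | 0.6 | 2.7 | 10.5 |

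Estimates of a true 1,450 average 1,449 to 1,451 throughout, so the arm contrast is not biased here.

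**4. Simulation, single observations removed and the mixed model refitted** (all data / 3 / 2.5 / 2 SD). Pairwise type I error is 5.2 / 5.6 / 6.9 / 9.3% with marginal residuals and 5.1 / 6.1 / 8.7 / 13.4% with conditional residuals. Coverage is 95.1 / 94.7 / 93.5 / 90.8% and 95.0 / 94.1 / 92.0 / 86.7%.

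**5. Cook's distance.** With equal arms and no covariate, every leverage is h = 1/75 and there are three parameters, so D = r²h / (3(1 − h)). The common rule D > 4/225 becomes r² > (4/225) × 3 × 74 = 3.947, or |r| > 1.987. That is the last column above. It is not a separate test of influence.

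**6. H1.1 under skewness.** Assume no true change and the same gamma distribution in all arms: shape 4, so skewness 2/√4 = 1, scaled to mean 0 and SD 2,500. The lower limit is −2 SD, so only the upper tail is cut. With known mean and SD:

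- 3 SD (gamma value above 10): tail contribution (4 × 0.02925 − 4 × 0.01034)/2 = 0.0378. The remaining mean is −0.0378/0.9897 = −0.0382 SD, about −96 steps/day.
- 2.5 SD (above 9): (4 × 0.05496 − 4 × 0.02123)/2 = 0.0675. The remaining mean is −0.0675/0.9788 = −0.0689 SD, about −172 steps/day.

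Simulation with estimated mean and SD gives −93 and −171, with rejection of about 13% and 25% at nominal 5%. The SE of the overall mean change is 2,500/√225 = 167, so these shifts are 0.56 and 1.02 standard errors. Right skew moves the estimate down, which would hide part of a real gain. Mirror-image skew would move it up by the same amount.

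**7. Gross device errors** (assumption: 2% of post-treatment values carry added error with SD 12,500). Power for 1,450 is 0.83 with all data and 0.93 after 3 SD removal, with type I error 4.9% and 5.6%. Huber regression on change scores, using all data, gives 0.92 and 5.1%.

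**The case against.** **The harm is small at a conventional cut-off.** This stands. At 3 SD fewer than one participant in 225 is expected to go, and type I error is 5.5-6.1%. The plan does not say 3 SD, however, and it names influential cases as a separate target.

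**Activity monitors produce gross errors, and removal protects against them.** This stands in part, as step 7 shows. It supports removing errors. It does not support removing valid values, and the plan already lists transformations and a Generalized Linear Model for poor fit. Robust regression recovered most of the power on change scores, but its performance within the planned mixed model has not been shown.

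**The analyst is blinded.** This limits selection by arm. It does not touch the mechanism in step 2.

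**The SAP is excerpted.** This stands as a limit of scope. A fuller source might hold a cut-off, and the finding covers only the supplied text.

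**Stronger readings the documents do not support.** A reader might infer that removal biases the comparison between arms, for example by deleting strong responders to one intervention. That needs a response distribution that differs by arm, and the documents give none. A reader might also infer that intent-to-treat is broken in every case. If only single observations are dropped, the mixed model keeps the participant's other values, so the loss of randomised people applies only to whole-participant removal. Nor do steps 2 to 5 measure the effect of an influence rule in the moderator models. Leverage varies there, and that was not simulated.

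**Conclusion.** The concern holds. The plan as written orders valid outcomes to be deleted from an analysis it calls intent-to-treat, and nothing in the supplied text limits the deletion to errors or provides an all-data result. Standard errors are then understated. The cost is small at 3 SD, moderate at 2.5 SD (type I error about 7-9%) and material at about 2 SD (about 9-13%, with coverage of about 87-91%). These figures assume normal data, the plan's design values and cut-offs the plan does not give. The H1.1 shifts assume a skewness of 1.

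Confidence is high that the rule should change. It does not extend to any particular size of harm. In particular, 11% or 13% should not be read as this trial's type I error, because the documents do not show that a cut-off near 2 SD was intended or used. The point should be fixed, and the repair is cheap.

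**What to change.** Replace the removal sentence with:

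> All valid observed data from randomised participants stay in the primary analysis. Values are corrected or set to missing only when judged, blind to arm and using the REDCap range checks and monthly review, to be device or recording errors. Non-normality is handled by the transformations or Generalized Linear Model already planned. A sensitivity analysis removes observations with absolute standardised residual above 3, and reports the number removed per arm.

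State whether these residuals are marginal or conditional, and take them from the final model after any transformation. A robust regression may be added as a further sensitivity analysis.

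The Updates refer to the end of the study, so the analysis may already have been run with removal. In that case, report the all-data analysis beside it, with the number removed per arm and the reasons.

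**Cost.** SAP wording and one extra analysis. On clean data the pairwise standard error is slightly wider (408 against 403 at 3 SD). If gross device errors go undetected, the all-data analysis loses precision (power 0.83 against 0.93 in the assumed 2% example).

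### For three arms and two time points, Bonferroni on between-arm contrasts that already follow a significant interaction test adds no needed error control and costs power on the main comparison

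*Combined protocol and SAP*

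**What the plan says.** The SAP, under General data management & analysis, sets the levels: "The alpha is set at 0.05 for primary analyses and .01 for secondary analyses". The same section gives the multiplicity rule, "Post-hoc tests in the GLMMs will use Bonferroni adjustment", and a separate rule for the moderator analyses: "for the regression models post-hoc probing of interactions will be done using simple slopes method". It does not say which tests form the Bonferroni family or what the divisor is.

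Under Expected outcomes and aim specific analysis, the model for H1.1 is a pre/post one: "A GLMM will be used to evaluate changes in SPD from pre- to post-training". Arms are reached through the interaction: "If an interaction is significant, the simple main effect of time will be compared between interventions". Aim 2 reuses the Aim 1 analyses for its own outcomes and adds: "Separate models will be completed for the 6 and 12 month time point".

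Power analysis & sample size gives 75 per arm to detect a differential increase "based on baseline steps/day and intervention received with power greater than 0.90". It mentions neither the preliminary interaction test nor Bonferroni. The research abstract in the protocol makes FAST+SAM against FAST and against SAM the specific objective.

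**The concern.** A between-arm contrast of change has to pass two hurdles: a significant interaction across the three arms, and then a Bonferroni-reduced level. For exactly three arms and one change per arm, the first hurdle is enough.

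- If all three arms are truly equal, any pairwise claim first requires the 2-df test to reject, which happens with probability 0.05.
- If exactly two arms are equal, only one true null hypothesis remains among the pairs, and it is tested at 0.05.
- If no two arms are equal, no false rejection is possible.

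A claim that FAST+SAM beats both single interventions also needs both contrasts to be significant, and such a joint requirement needs no adjustment. Bonferroni is then a strictly weaker rule for these contrasts, and the power it gives up belongs to the comparison the trial was designed to make.

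**Working it through.** **Inputs** (Power analysis & sample size): 75 per arm; SD of steps/day 2,500; correlation of repeated measures 0.50; gains of about 1,700 for FAST+SAM and 250 for FAST in participants with low baseline steps; overall gains of about 1,000 for FAST and 1,100 for SAM. Alpha 0.05 is from General data management & analysis.

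**Assumptions:** two-sided tests; Bonferroni divisor 3 (all pairs) or 2 (FAST+SAM against each single arm), both shown; gains applied to whole arms, only to compare the two rules.

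**Plan's own figure.** SD of change = 2,500 × √(2 × (1 − 0.50)) = 2,500. SE of a difference between two arms = 2,500 × √(2/75) = 408. The largest planned difference is 1,700 − 250 = 1,450, and 1,450/408.2 = 3.552. Power at 0.05 = Φ(3.552 − 1.960) = 0.944, which agrees with a figure above 0.90. This reproduces it only as a single FAST+SAM v FAST contrast, unadjusted, with no preliminary test, and with every participant showing the low-baseline effect. Power for the baseline-dependent effect itself cannot be recomputed, because no baseline distribution is given.

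**Family-wise error of the between-arm contrasts** (1,000,000 simulated trials, pooled variance, 222 error df, 2-df F test at 0.05):

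| Rule | All arms equal | Two arms equal, third 1,700 higher |
|---|---|---|
| Pairwise tests at 0.05, no preliminary test | 0.122 | 0.050 |
| 2-df test, then unadjusted pairs | 0.050 | 0.050 |
| 2-df test, then Bonferroni, divisor 3 | 0.042 | 0.017 |

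The second row already meets 0.05.

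**Chance that FAST+SAM beats both single arms, after the 2-df test:**

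| Gains (FAST+SAM/FAST/SAM) | Unadjusted | Divisor 2 | Divisor 3 |
|---|---|---|---|
| 1,700/250/1,100 | 0.306 | 0.214 (−30%) | 0.172 (−44%) |
| 1,700/1,000/1,100 | 0.190 | 0.122 (−36%) | 0.091 (−52%) |
| 1,700/250/250 | 0.898 | 0.835 (−7%) | 0.790 (−12%) |

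The preliminary test costs little on this joint claim. Without it, the unadjusted figures in the first two rows are 0.307 and about 0.198.

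**The single FAST+SAM v FAST contrast of 1,450:**

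| Setting | Unadjusted | Divisor 2 | Divisor 3 |
|---|---|---|---|
| No preliminary test, SD 2,500 | 0.944 | 0.905 | 0.877 |
| No preliminary test, baseline-adjusted SD 2,500 × √(1 − 0.50²) = 2,165 | 0.984 | 0.969 | 0.956 |
| After the 2-df test, SD 2,500, SAM gains 1,100 | 0.893 | 0.883 | 0.869 |

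**Within-arm tests.** Suppose the simple effects of time are pre/post tests within each arm, with two arms unchanged and one improved by 1,700 or 3,000. Unadjusted tests after the 2-df test then have family-wise error 0.096 to 0.098, and divisor 3 brings this to 0.032 to 0.033. The closed-test argument does not cover these tests, and Bonferroni does needed work there.

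**The case against.** Bonferroni after an omnibus test is valid and conservative, so nothing in the plan inflates error; the change is a gain in efficiency. That stands, but the gain costs nothing in error control and falls on the study objective.

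The interaction step is printed only for H1.1, which is about improvement in all three arms. The SAP is an excerpt and refers to further hypotheses that it does not print. That stands as a limit: the sequence is documented for H1.1 and carried to Aim 2, and it is inferred for any separate superiority hypothesis.

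The loss depends on the divisor and the scenario, and is modest if both single arms gain 250. The first scenario also mixes low-baseline figures for FAST+SAM and FAST with an overall figure for SAM. And even unadjusted, the joint claim has a chance of only 0.19 to 0.31 when SAM gains 1,100, so Bonferroni is not the main limit on power. All of this stands, and it is why the size is given as a range.

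A reader might infer that Bonferroni pushes the stated power below 0.90. The documents do not support this. It requires divisor 3, which is not stated, together with change-score variance. With SAM at 1,100, the preliminary test alone already brings the contrast to 0.893. The stated power is also for an effect that differs by baseline steps, not for a whole-arm contrast.

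A reader might also infer that Bonferroni is redundant throughout. The sentence covers every GLMM post-hoc test, and the within-arm result above shows why that goes too far.

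**Conclusion.** The point holds for pairwise between-arm contrasts of change in a three-arm model with two time points. There, Bonferroni after a significant 2-df interaction test adds no error control that is needed. It reduces the chance of showing FAST+SAM better than both single arms by 30% to 52% in relative terms when SAM gains the planned 1,100, and by 7% to 12% if both single arms gain only 250.

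This rests on the plan's 75 per arm, SD 2,500 and correlation 0.50, on two-sided tests, on divisor 2 or 3, and on each model having one change per arm. It does not extend to within-arm tests or to the moderator regressions, which have their own simple-slopes rule with no Bonferroni stated. It does not show that the printed power is wrong. It shows that the power section does not describe the two-step, adjusted contrasts the SAP would run.

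**What to change.** Limit the Bonferroni sentence to within-arm pre/post tests and other GLMM post-hoc tests, and add:

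> For pairwise between-arm contrasts of change in a three-arm model with two time points, after a significant 2-df arm-by-time test, contrasts are tested at the same alpha without further adjustment (closed test). Superiority of FAST+SAM over both single interventions requires both contrasts to be significant.

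Leave the simple-slopes rule for the regression models as it is. If Bonferroni is kept for the arm contrasts, name the family and the divisor, and restate power for the contrasts as they will be tested, that is, after the interaction test and with the adjustment.

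The cost is one amended and one added passage in the SAP. Sample size and data collection are unaffected, and family-wise error for the arm contrasts stays at 0.05.
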